8.4 UNANTICIPATED PROBLEMS

8.4.1 DEFINITION OF UNANTICIPATED PROBLEMS (UP)

The Office for Human Research Protections (OHRP) considers unanticipated problems involving risks to participants or others to include, in general, any incident, experience, or outcome that meets all of the following criteria:

- Unexpected in terms of nature, severity, or frequency given (a) the research procedures that are described in the protocol-related documents, such as the Institutional Review Board (IRB)-approved research protocol and informed consent document; and (b) the characteristics of the participant population being studied;
- Related or possibly related to participation in the research (“possibly related” means there is a reasonable possibility that the incident, experience, or outcome may have been caused by the procedures involved in the research); and
- Suggests that the research places participants or others at a greater risk of harm (including physical, psychological, economic, or social harm) than was previously known or recognized.

This definition could include an unanticipated adverse device effect, any serious adverse effect on health or safety or any life-threatening problem or death caused by, or associated with, a device, if that effect, problem, or death was not previously identified in nature, severity, or degree of incidence in the investigational plan or application (including a supplementary plan or application), or any other unanticipated serious problem associated with a device that relates to the rights, safety, or welfare of subjects (21 CFR 812. 3(s)).

8.4.2 UNANTICIPATED PROBLEM REPORTING

The investigator will report unanticipated problems (UPs) to the reviewing Institutional Review Board (IRB) and to the Data Coordinating Center (DCC)/lead principal investigator (PI). The UP report will include the following information:

- Protocol identifying information: protocol title and number, PI's name, and the IRB project number;
- A detailed description of the event, incident, experience, or outcome;
- An explanation of the basis for determining that the event, incident, experience, or outcome represents an UP;
- A description of any changes to the protocol or other corrective actions that have been taken or are proposed in response to the UP.

To satisfy the requirement for prompt reporting, UPs will be reported using the following timeline:

- UPs that are serious adverse events (SAEs) will be reported to the IRB and to the DCC/study sponsor within 24 hours of the investigator becoming aware of the event.
- Any other UP will be reported to the IRB and to the DCC/study sponsor within 7 days of the investigator becoming aware of the problem.
- All UPs should be reported to appropriate institutional officials (as required by an institution's written reporting procedures).

8.4.3 REPORTING UNANTICIPATED PROBLEMS TO PARTICIPANTS

If an unanticipated problem occurs that places a participant at greater risk than originally anticipated, participants will be notified. Changes in risk profile or study design affecting participant safety will be addressed via protocol amendment. This information would be reviewed with active subjects who would be asked to sign the amended consent to continue study participation.

9 STATISTICAL CONSIDERATIONS

9.1 STATISTICAL HYPOTHESES

The primary hypothesis is that quadriceps strength symmetry will be greater with the combination of NMES and ECC relative to the placebos at both 9 months and 18 months post-ACLR. Statistically, the following null and alternative hypotheses will test the superiority of the combination of NMES + ECC versus placebo arm in the change from baseline to 9 months and 18 months post-ACLR in isokinetic quadriceps strength symmetry index separate analyses:

$$\begin{aligned} H_01: \Delta_{9\text{mo}} \text{ NMES + ECC} &\leq \Delta_{9\text{mo}} \text{ NMES placebo + ECC placebo} \\ H_{A1}: \Delta_{9\text{mo}} \text{ NMES + ECC} &> \Delta_{9\text{mo}} \text{ NMES placebo + ECC placebo} \\ H_{06}: \Delta_{18\text{mo}} \text{ NMES + ECC} &\leq \Delta_{18\text{mo}} \text{ NMES placebo + ECC placebo} \\ H_{A6}: \Delta_{18\text{mo}} \text{ NMES + ECC} &> \Delta_{18\text{mo}} \text{ NMES placebo + ECC placebo} \end{aligned}$$

where Δ reflects the adjusted mean change from baseline at 9 or 18 months post-ACLR in isokinetic quadriceps strength symmetry index.

9.2 SAMPLE SIZE DETERMINATION

For the main study objectives, the sample size of 112 participants (56 per each of the 2 treatment groups) allows sufficient power to test the primary hypotheses regarding two separate comparisons (each co-primary endpoint) of the combination NMES + ECC vs NMES placebo + ECC placebo. Each test will be conducted using a two-sided 0.025 Type I error level ($=0.05/2$, the Bonferroni adjustment for two comparisons). We hypothesize that the effect size (treatment difference / standard deviation) will be at least 0.7 for the tests of NMES + ECC vs NMES placebo + ECC placebo. Assuming 20% drop-out (resulting in an effective sample size of 45 per group), we have at least 80% power to detect this effect size. Preliminary data from the

same site with a comparable patient population and primary endpoint demonstrated a 1.14 effect size. Because of the small sample size and variability in measurements in this preliminary study, we conservatively reduced the effect size for this study.³⁵

An additional cohort of 28 participants will be studied – the SOC control group. The sample size of 28 participants for this group is based on feasibility considerations.

Thus, the total sample size for the trial is 140 participants.

9.3 POPULATIONS FOR ANALYSES

Several analysis sets will be used in analyses:

- The main population for efficacy will be the modified intention-to-treat population (mITT), defined as all participants randomized and receiving at least one study intervention. Subjects will be analyzed by assigned treatment.
- A second analysis set will be used to assess the robustness of the primary conclusions in the subset of participants in the mITT analysis set. This set contains participants who complied with the protocol sufficiently to ensure that these data would be likely to represent the effect of treatment according to the underlying scientific model. The Per Protocol (PP) analysis set will consist of all subjects in the mITT population who do not have a major protocol violation, inclusive of violation of entry criteria.
The Safety Population is defined as all participants who are randomized and receive at least study intervention. The Safety Population will be used for all safety analyses. Subjects will be analyzed by assigned treatment.
- All participants in the SOC control group will be included in the exploratory analyses.

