1.2 SCHEMA – TREATMENT GROUPS

1.3 SCHEMA – SOC CONTROL GROUP

1.4 SCHEDULE OF ACTIVITIES (SOA)

Procedures	Pre-Screening (Phone and Record Review)	Testing Visit 1 Enrollment/BaseLine	Repeat Testing Visit 1 ^d	ACL Surgery	Intervention or SOC PT Visits 1-16 ^f	Testing Visit 2 Post-NMES Intervention	Intervention or SOC PT Visits 17-32 ^g	Testing Visit 3 Post-ECC Intervention	Testing Visit 4 9 months post-ACLR ^c	12 months post-ACLR	15 months post-ACLR	Testing Visit 5 18 months post-ACLR ^c
Days on Study (relative to ACLR)	-365	-30	-30	0	1-70	N/a ^h	56-126	N/a ^h	270	365	455	540
Visit Window (days)- Treatment Group	0	0	0	0	0	+7	0	+7	±30	±14	±14	±30
Informed consent/assent	X											
Inclusion/Exclusion	X	X	X	X								
ACL Reconstruction Surgery					X							
Demographics		X										
Medical history		X	X									
Clinical Knee X-ray Record Review		X										
Pregnancy test ^a		X	X									
Randomization ^b					X							
Concomitant medication review	X											X
Administer NMES or placebo ^e					X							
Administer ECC or placebo ^e							X					
Standard of Care Rehabilitation monitoring					X			X				
Height & Weight	X	X							X			X
Assessment of Adverse Events	X											X
Knee X-ray		X	X									X
Knee MRI												X
Quadriceps/Knee Ultrasound		X	X			X		X	X			X
Thigh Muscle Strength Assessment		X	X			X		X	X			X
Quadriceps Activation Assessment		X	X			X		X	X			X
Physical Activity Monitoring										X	X	
Questionnaires		X	X			X		X	X			X
Gait Biomechanics		X	X						X			X
Clinical Hop Testing									X			X
Hopping Biomechanics									X			X
Optional Muscle Biopsy		X	X					X				X

^a Urine pregnancy test for women of child bearing potential

^b Randomization will occur after ACL reconstruction and implemented at first intervention visit. SOC control group will not be randomized.

^c Testing procedures will be scheduled within a 30 day window before or after 9 and 18 month testing date

^d Completed if Testing Visit 1 falls out of window

^e Does not apply to SOC control group

^f Intervention or SOC PT visits 1-16 can take place beginning on post-op day 1 but may begin up to 2 weeks after surgery.

^g Intervention or SOC PT visits 17-32 can take place beginning on day of Testing Visit 2 but may begin up to 2 weeks following that visit.

^h Testing Visit 2 and 3 will take place within 7 days of the last intervention or SOC PT visit.

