Protection/Mitigation of Risk 3: In order to minimize this risk, no ACLR participant will be allowed to undergo biomechanical testing unless cleared by their physician to do so. If injury were to occur during test, the study team would manage the injury and will then refer the participant to Drs. [name] or [name] for follow-up. It is important to note that volunteers will not be performing the landing procedures until 9 months after ACL reconstruction (i. e., when the volunteer would typically be released to return to sport or activity).

Risk 4: Any risk specific to musculoskeletal imaging (i.e. , X-ray and MRI) including discomfort while lying in the scanner (MRI), exposure to radiation (X-ray), and exposure to loud noises (MRI).

Protection/Mitigation of Risk 4: All appropriate precautions that occur with standard clinical imaging will take place (e. g. , use of lead vests for X-ray, ear plugs or equivalent for MRI).

Risk 5: Any risk related to topical application of tape or electrical stimulation pads, which could occur secondary to all study procedures, such rash or itching.

Protection/Mitigation of Risk 5: If irritation secondary to application of tape or electrical stimulation electrodes would occur, we would treat with topical hydrocortisone. If rash/irritation did not improve (or appeared to be something more severe), we would refer to Drs. [name] or [name] for evaluation and treatment.

Risk 6: Any risk specific to the ACL reconstruction, including infection, cyclops lesion, deep vein thrombosis, damage to nerves/vessels, cellulitis, hemarthrosis requiring arthrocentesis, septic arthritis, pain not controlled with analgesics, as well as risks associated with anesthesia (e. g. , nausea and vomiting).

Protection/Mitigation of Risk 6: This risk/event will be captured as the ACLR will occur after participants have signed informed consent/assent. If any of these were to occur or we noticed signs or symptoms of any of these conditions, we would refer to Drs. [name] or [name] for immediate follow-up.

Risk 7: Any risk related to the muscle biopsy including discomfort, infection, bruising, and/or blood clot.

Protection/Mitigation of Risk 7: A sterile environment will be used to collect biopsy samples in

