8.3.5 TIME PERIOD AND FREQUENCY FOR EVENT ASSESSMENT AND FOLLOW-UP

A consistent methodology for eliciting AEs will be used at all subject evaluation time points that includes open-ended questions such as:

- “How have you felt since your last clinical visit?”
- “Have you had any new or changed health problems since you were last here?”

The occurrence of an adverse event (AE) or serious adverse event (SAE) may come to the attention of study personnel during study visits and interviews of a study participant presenting for medical care, or upon review by a study monitor. AEs may also be identified through medical record review or through physician evaluation.

All AEs including local and systemic reactions not meeting the criteria for SAEs will be captured on the appropriate case report form (CRF). Information to be collected includes event description, time of onset, clinician's assessment of severity, relationship to study product (assessed only by those with the training and authority to make a diagnosis), and time of resolution/stabilization of the event. All AEs occurring while on study must be documented appropriately regardless of relationship. All AEs will be followed to adequate resolution.

Any medical condition that is present at the time that the participant is screened will be considered as baseline and not reported as an AE. However, if the study participant's condition deteriorates at any time during the study, it will be recorded as an AE.

Changes in the severity of an AE will be documented to allow an assessment of the duration of the event at each level of severity to be performed. AEs characterized as intermittent require documentation of onset and duration of each episode.

All reportable events with start dates occurring any time after informed consent is obtained until the last study visit (i.e. 18 month study visit). At each study visit, the investigator will inquire about the occurrence of AE/SAEs since the last visit. Events will be followed for outcome information until resolution or until last study visit. In the event that an AE or SAE occurred at the last study visit it would be followed for 7 days (non-serious AEs) or 30 days (serious AEs) after said study visit.

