8.3.8 SERIOUS ADVERSE EVENT REPORTING

All SAEs will be mapped to system organ classes (SOC) using preferred MedDRA SOC terms, graded for severity and relationship to study drugs as detailed above, and recorded with start dates occurring any time after informed consent is obtained until 30 days after the last day of study participation. At each study visit, the investigator or designee will inquire about the occurrence of SAEs since the last visit and study participants, and their significant others will be asked in advance to notify the study investigators immediately regarding any hospitalization, serious change in their health or in the event of a death. Events will be followed for outcome information until resolution or stabilization, with stop dates recorded for resolution.

Regardless of whether the SAE is deemed related to use of the study interventions, the data for the SAE must be reported with the appropriate information by the study investigators or their designee to the Data Coordinating Center within 24 hours of learning of the event. In addition, new follow-up data must be reported within 24 hours of receipt. The designated study medical monitor, [name], DO, or designee may be contacted at any time for immediate discussion regarding such an event.

Hospitalizations for the following reason, which are not related to an AE, do not require reporting:

- Hospitalization or prolonged hospitalization for diagnostic or elective surgical procedures for preexisting conditions.

When recording a death, the event, or condition that caused or contributed to the fatal outcome should be reported as the single medical concept. If the cause of death is unknown and cannot be ascertained at the time of reporting, the report will be identified as an "Unexplained Death".

Investigators must report all SAEs to their governing IRB/IEC, as required by local regulations and guidelines.

A record of all SAEs, by study subject and preferred SOC terms will be recorded centrally by the DCC.

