9.4.4 SAFETY ANALYSES

Safety analyses will be performed on the safety analysis set. Safety data, including frequency of events and proportion of participants experiencing events (e.g., serious adverse events, adverse events leading to early discontinuation of study intervention), will be summarized descriptively overall and by treatment group. For categorical safety outcomes, numbers and percentages will be used. For continuous safety outcomes, number, mean, standard deviation, median, interquartile range, minimum and maximum will be used to summarize changes from baseline to each study visit in vital signs.

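### Safety analyses set no onset cut-off for the by-arm tables, group by assigned treatment, and plan no safety summary for the SOC group

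*Combined protocol and SAP*

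**What the plan says.** **Set and grouping.** Section 9.3: "The Safety Population is defined as all participants who are randomized and receive at least study intervention" (evidently at least one intervention). It continues: "The Safety Population will be used for all safety analyses. Subjects will be analyzed by assigned treatment".

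**Tables.** Under Section 9.4.4, event frequencies and proportions of participants "will be summarized descriptively overall and by treatment group". The section states no onset window, either to include or to exclude events before randomisation.

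**Collection window.** Section 8.3.5 covers "All reportable events with start dates occurring any time after informed consent is obtained until the last study visit". For serious events, Section 8.3.8 has them "recorded with start dates occurring any time after informed consent is obtained until 30 days after the last day of study participation".

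**Order of events.** On surgical complications, Section 2.3.3 (Risk 6) says: "This risk/event will be captured as the ACLR will occur after participants have signed informed consent/assent". Section 1.4 says: "Randomization will occur after ACL reconstruction and implemented at first intervention visit". Its footnote on the first block of visits says that they "can take place beginning on post-op day 1 but may begin up to 2 weeks after surgery". Baseline testing, with an optional muscle biopsy, comes before surgery.

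**SOC group.** Section 9.4.9 lists baseline variables and the co-primary and key secondary endpoints for this group. It lists no safety summary.

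**Related provisions.** Graft failure is the only event of special interest and goes to the DSMB as a count per study group (Section 8.3.7). The eCRF holds each event's onset date (Section 8.3.6), and severity changes are documented (Section 8.3.5). A separate SAP is still to be written (Section 9.4).

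**The concern.** A by-arm safety table should show what happened after the arms began to differ, according to what people received. These rules do not secure that.

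- **Onset.** Events before the first session cannot be caused by the arm. Section 2.3.1 lists hemarthrosis under both the eccentric exercise risks and the surgical risks, so without a date rule that line can mix the two sources. Relatedness grading is a judgement, and Section 9.4.4 does not restrict the tables to related events.
- **Grouping.** The Safety Population is in effect the mITT set under another name. A participant treated with the other arm's programme would have any harm counted under the wrong exposure.
- **SOC group.** Section 8.3.3 accepts that either the active or the placebo interventions might compromise the graft. Harm common to both arms cannot appear in the randomised contrast. Only the SOC group goes without study intervention.

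At stake is how readable the harm data are in a trial with 56 per arm and descriptive safety only. The primary efficacy conclusion is not involved.

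**Working it through.** **The plan's own figure.** The documents give no safety rate or power. The efficacy power reproduces: with 45 per arm, effect size 0.7 and two-sided 0.025, Φ(0.7 × √(45/2) − 2.241) = Φ(1.079) = 0.86, against a claim of at least 80%. It has no bearing on safety.

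**Inputs.** 56 per arm and 28 SOC participants (Section 9.2); about 10% graft failure under standard rehabilitation (Section 8.3.3). *Assumptions:* post-intervention risks of 10% (borrowed from the graft-failure figure) and 20%; a pre-randomisation risk q equal in both arms and independent of later events.

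**1. No onset cut-off.** Any-event risk = 1 − (1 − q)(1 − p), with p = 0.10 or 0.20.

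| q | Lower-risk arm | Higher-risk arm | Difference (points) | Ratio |
|---|---|---|---|---|
| 0 | 10.0% | 20.0% | 10.0 | 2.00 |
| 5% | 14.5% | 24.0% | 9.5 | 1.66 |
| 10% | 19.0% | 28.0% | 9.0 | 1.47 |
| 20% | 28.0% | 36.0% | 8.0 | 1.29 |
| 30% | 37.0% | 44.0% | 7.0 | 1.19 |

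The difference shrinks by the factor (1 − q). For mean event counts per person, with q now the mean number of earlier events, the expected difference stays at 0.10 and only the ratio falls: (0.20 + q)/(0.10 + q) is 1.50 at q = 0.1 and 1.33 at q = 0.2.

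Noise: the between-arm difference in earlier events has mean zero and standard error √(2q(1 − q)/56). At q = 10% this is √(0.18/56) = 0.057, or 5.7 points, beside an assumed signal of 10.

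**2. Assigned against received.** If a fraction x of each arm receives the other treatment, the difference is 10 × (1 − 2x) points: 9.6 at x = 2%, 9.0 at 5%, 8.0 at 10%. At x = 0 the two groupings coincide.

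**3. SOC group.** Leaving it out changes the randomised contrast by exactly 0. As a reference it would be imprecise: 28 × 0.10 = 2.8 expected graft failures. For 3/28 (10.7%) the exact 95% interval is about 2% to 28%. The chance of no failure at all is 0.9^28 = 5.2%.

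**The case against.** The case for leaving the plan alone has real content.

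- **Sections 8.3.5 and 8.3.8 govern collection, not tabulation.** A reader might infer that the by-arm tables count every event since consent. Section 9.4.4 does not say so; it is silent. Onset dates exist and a SAP is to follow, so a later subset is possible. This stands: the gap is an unstated cut-off. But the SAP does not dispose of the point, because Section 9.3 already fixes the set and the grouping.
- **Surgical events do not hide graft damage.** A reader might infer that they do. Graft failure is counted and reported separately, and events that stop the intervention follow its start by definition. This stands.
- **Earlier events are balanced in expectation.** They dilute; they do not favour an arm or erase a difference. This stands.
- **Wrong-arm delivery may never occur.** Therapists are given the allocation (Section 6.2), and sessions are in person with intensity recorded (Section 6.3). In the first two weeks both arms have stimulation at the maximum tolerated (Section 6.1.2). Sections 6.1.2 and 7.1 also allow reduced dose or partial treatment, so *received* needs a definition. This stands, and limits the grouping point to a safeguard.
- **The SOC group is small, non-randomised and made up of people who declined the trial.** Section 4.1 already describes the placebo arm as standard of care, and Section 9.3 places all SOC participants in exploratory analyses. So a reader should not conclude that their events can never be tabulated, or that omitting them dilutes the randomised contrast. What remains is that no safety summary is listed for the one group without study intervention.

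**Conclusion.** The point holds as a should-fix matter of definition.

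Under the assumed risks of 10% and 20%, shared earlier risks of 5% to 30% would leave a ratio of 1.66 to 1.19 in place of 2.00, and a difference of 9.5 to 7.0 points in place of 10.0. These rates illustrate the mechanism and are not trial estimates. The direction is always towards the null, in ratios and any-event differences alone. The documents do not support a claim that real differences in harm would be lost.

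The grouping rule costs nothing if nobody receives the wrong programme, and 0.2 points of a 10-point difference for each 1% of each arm that does.

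The missing SOC summary removes the only in-trial comparison without study intervention for harm common to both arms. It would be a weak reference. Besides its size, Section 8.1 places the event review at intervention visits under a heading limited to randomised participants, so ascertainment in the SOC group may be less frequent. Graft failure, diagnosed by the patient's physician, should suffer least from that.

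**What to change.** Amend Sections 9.3, 9.4.4 and 9.4.9, and carry the same wording into the SAP before unblinding:

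1. **Onset.** By-arm tables count events that start or worsen on or after the first study session. Events from consent to that session go in a separate table.
2. **Grouping.** Analyse safety by treatment actually received, with assigned arm as a check. Define *received* by the arm's programme as delivered, so that a dose reduced for tolerance stays under that programme. Do not define it by an intensity threshold: Sections 1.1, 4.3 and 6.1.2 give different figures for the placebo eccentric intensity, and those passages must be reconciled.
3. **SOC group.** Add a separate descriptive safety summary, including graft failure, counted from the matching post-operative time (for example the first SOC physical therapy visit, which Section 1.4 puts in the same window). Label it non-randomised, show intervals, and note any difference in how often events were asked about.

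Cost: one flag derived from dates already on the eCRF, one or two extra tables, and a written rule for anyone who received both arms' treatment. No new data collection is needed, and the efficacy analysis is untouched.
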